### **RA Disease Duration**

The RA disease duration is the number of years from the date of diagnosis of RA to the date of randomization, which will be derived based on the table below. No imputation will be done for disease diagnosis date, but to avoid a disease duration of zero, 1 month (or 1/12 years) may be added.

**Table 1 Calculation of the Duration of RA**

Observed portion	Missing portion	Formula to Calculate Duration
Year, Month, Day		(Date of Randomization – Date of RA Diagnosis + 1)/365.25
Year, Month	Day	[Year(Date of Randomization)-Year(Date of RA Diagnosis)]+ [Month(Date of Randomization)-Month(Date of RA Diagnosis)]/12*
Year	Month, Day	[Year(Date of Randomization)-Year(Date of RA Diagnosis)] *

\*If the duration equals 0, add 1 month or 1/12 years.

### **Seropositivity**

For seropositivity summary at baseline, a normal or negative baseline result for RF would be <12 IU/mL and for CCP3 would be <20 Units based on the laboratory assay maker’s guidance.

### **Study Day 1**

Study Day 1 is defined as the first day of IP administration. For subjects who are randomized but not dosed after the randomization, study day 1 is defined as the date of randomization.

### **Study Day**

Study day is defined as the number of days from Study Day 1.

- Before Study Day 1:

Sponsor: Amgen Inc.

Statistical Analysis Plan

Protocol No: 20130108

10-December-2018/ Version 2.0

---

Study Day = (Date of Interest – Date of Study Day 1)

- On or After Study Day 1:

Study Day = (Date of Interest – Date of Study Day 1) + 1

Therefore the day prior to Study Day 1 is -1.

### **Study Randomization**

Study randomization is defined as when subject receives a random treatment allocation via the IXRS system.

### **Study Visit**

Since the actual visit for a subject may not exactly coincide with their scheduled visit date, the actual visit date is mapped to the study analysis visit as follows. Note that the following analytical visit windows for statistical analysis are different from the ones defined in Section 18.0 of the IXRS Business Requirement. The actual visit date is allowed to fall within specified interval of the target day.

In general, if more than one actual visit (including the unscheduled visits) falls within the same defined window, the visit closest to the target day with non-missing data will be considered for analysis. If two actual visit dates are at the same distance from the target day, the latest visit with non-missing data will be considered for analysis. For Week 24, only actual visits that occur before or on same date as first infusion of second dose should be considered.

The rules above for selecting a visit from multiple ones within the same visit window are not applicable to retest values of lab data. If the lab measurement is a retest, the retest value will be chosen.

PK concentration will be summarized by the scheduled sample visit in the protocol. For PK concentration collected in the unscheduled visits or in the early discontinuation study visit, the associated scheduled sample visit is defined as below. If multiple records are assigned to the same visit, the one closest to the reference date/time will be selected into the summary.

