IgA, IgG, and IgM levels		X				X ⁱ	X ⁱ								X		X					X
Urinalysis	X	X						X									X					X
Tuberculosis testing	X																					
Pregnancy ^j	X	X						X								X	X			X	X	
Anti-CCP	X																					
Rheumatoid factor	X																					

Page 2 of 2

AE = adverse event; BL = Baseline; CRP = C-Reactive Protein; EOI = End of Infusion; EOS = End of Study; ESR = Erythrocyte sedimentation rate; h = hour; HAQ-DI = Health Assessment Questionnaire – Disability Index; HBsAg = Hepatitis B surface antigen; Anti-HBc = Hepatitis B core antibody; HCV = Hepatitis C virus antibody; Ig = Immunoglobulin, PK = Pharmacokinetic; Scn = Screening; VAS = Visual analogue scale; Anti-CCP= Anti-cyclic citrullinated peptide antibody

^a The second dose will be administered at week 24 or earlier, ie, anytime from week 16 to week 24, in individual subjects, if necessary in the opinion of the Investigator. For subjects who receive retreatment before week 24, all week 24 and post-week-24 assessments will be moved up to the corresponding time point after treatment (eg, week 26 will be 2 weeks after retreatment, week 30 will be 6 weeks after retreatment, etc.). An infusion may be delayed up to 7 days to allow for recovery from infection.

^b Subjects early terminating study should perform week 48 procedures.

^c Historical radiograph performed within 3 months prior to first dose of IP may be used and does not need to be repeated at screening ([section 10.7](#) for details)

^d ABP 798/rituximab dosing to be administered after all other procedures are completed for each visit.

^e Subjective assessments will be the first procedures performed at the visit.

^f Includes any other lab tests required only for screening. Creatinine clearance calculation will be performed only at screening.

^g Either CRP or ESR is required at screening. CRP will be performed by central lab and results will be blinded to study sites. ESR will be performed by local laboratory.

^h PK sampling: day 1, predose, at EOI, and 3 and 6 hours postdose; day 2 (24 hours postdose); day 3 (48 hours postdose); day 15, predose, at EOI, and 3, 6, and 24 hours postdose (day 16), and 48 hours postdose (day 17). In addition, at week 4 (day 29), week 8 (day 57), week 12 (day 85), and predose week 24, week 26, and week 30, 48/EOS. Blood sampling for PK analysis during each return visit, including the EOS visit, will occur per the scheduled time point with tolerance collection

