9.13 Week 30 (\pm 2 days)

Thirty weeks (\pm 2 days) after the first infusion (or 6 weeks after initiation of retreatment if retreatment occurred before week 24), the subject will return to the study site. The following assessments/procedures will be performed at week 30:

- vital signs (systolic and diastolic blood pressure, pulse, respiration rate, and temperature)
- collection of PK samples and samples for antidrug antibodies

Any changes in concomitant medications since the last assessment will be recorded. All AEs, including increases in severity or frequency of pre-existing conditions, will be recorded in the eCRF. SAEs will be reported as outlined in [Section 11.2.2](#).

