9.14 Week 40 (\pm 3 days)

Forty weeks (\pm 3 days) after the first infusion (or 16 weeks after initiation of retreatment if retreatment occurred before week 24), the subject will return to the study site. The following assessments/procedures will be performed at week 40:

- subjective assessments (Subject's Global Health Assessment, subject's assessment of pain, and HAQ-DI, [Section 17.4](#)); subjective assessments will be the first assessments performed at the visit
- joint assessments (DAS and ACR tender/swollen joint counts; [Section 17.3](#))
- Investigator's Global Health Assessment
- clinical laboratory testing, including serum chemistry, hematology, and CRP
- urine pregnancy test (for women of childbearing potential)

Any changes in concomitant medications since the last assessment will be recorded. All AEs, including increases in severity or frequency of pre-existing conditions, will be recorded in the eCRF. SAEs will be reported as outlined in [Section 11.2.2](#).

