9.15 Week 48 (EOS)

Forty-eight weeks (\pm 2 days) after the first infusion (or 24 weeks after initiation of retreatment if retreatment occurred before week 24) or at the time of early discontinuation, the subject will return to the study site for a follow-up assessment. The following assessments/procedures will be performed at week 48/EOS:

- subjective assessments (Subject's Global Health Assessment, subject's assessment of pain, and HAQ-DI; [Section 17.4](#)); subjective assessments will be the first assessments performed at the visit
- Investigator's Global Health Assessment
- physical examination, including evaluation of body systems
- vital signs (systolic and diastolic blood pressure, pulse, respiration rate, and temperature)
- joint assessments (DAS and ACR tender/swollen joint counts; [Section 17.3](#))
- clinical laboratory testing, including serum chemistry, hematology, and CRP
- urinalysis and urine pregnancy (for women of childbearing potential)
- collection of PK samples (PK sample must be within 2 days of week 48) and samples for antidrug antibodies, CD19+ cell count, and IgA, IgG, and IgM levels

Any changes in concomitant medications since the last assessment will be recorded. All AEs, including increases in severity or frequency of pre-existing conditions, will be recorded in the eCRF through the week 48/EOS visit. SAEs will be reported as outlined in [Section 11.2.2](#). Any SAEs ongoing at week 48/EOS will be followed until they resolve or are considered chronic or stable.

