**FOR SAFETY (HEMATOLOGY AND CHEMISTRY) ANALYSES:**

Study Analysis	Target Day	Study Day	Interval (days)
Visita			
Baseline b	1	≤1	NA
Week 2	15	2 – 16	15
Day 17	17	17	1
Week 4	29	18 – 42	25
Week 8	57	43 – 105	70
Week 24	169	106 – 175	63
Week 26	183	176 – 196	21
Week 30	211	197 – 245	49
Week 40	281	246 – 308	63
Week 48	337	≥309	NA

a Laboratory parameters will only be included at the visits where it is scheduled for assessment in the output tables.

b If a subject has lab measurements on the same day as the first infusion date of first dose but at a time after the first infusion of first dose is administered, the lab measurements will not be defined as baseline, but as Week 2 measurements.

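### SAP visit windows outside PK count from Day 1, while the protocol times weeks 26 to 48 from an early second dose; late visits are then relabelled or lost in descriptive by-visit outputs

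*SAP*

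**What the plan says.** **Protocol.** The second dose may start at any time from week 16 to week 24. For a subject retreated early, Table 1 footnote a says that "all week 24 and post-week-24 assessments will be moved up to the corresponding time point after treatment". Section 9.14 places the week-40 visit at week 40, "or 16 weeks after initiation of retreatment if retreatment occurred before week 24". Section 9.15 places EOS at week 48, "or 24 weeks after initiation of retreatment if retreatment occurred before week 24". Weeks 26 and 30 move in the same way, to 2 and 6 weeks after retreatment starts (9.12, 9.13).

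**SAP.** Section 5.1 fixes the clock: "Study day is defined as the number of days from Study Day 1", and Day 1 is the first IP administration. The windows for efficacy, hematology and chemistry, CD19/Ig, ADA, and vital signs from week 24 on are ranges of that study day. When several visits share a window, "the visit closest to the target day with non-missing data will be considered for analysis"; a tie goes to the later visit. The only retreatment rule in this mapping bars visits after the second dose from week 24. By contrast, the PK windows for weeks 24 to 48 are tied to the second-dose infusions.

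Section 9 makes these derived visits the default for every by-visit summary. Section 9.7 runs the Day 1 to EOS efficacy analyses for all subjects and, separately, without early retreatment (second dose before day 162).

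**The concern.** The two documents use different clocks for the same visits. If retreatment is early enough, a visit that the protocol calls week 48 lands in the SAP's week-40 window, or in a stretch of days that no window covers. The all-subjects week-40 column then mixes responses 16 and 24 weeks after the second dose, and early-retreated subjects drop out of week 48. Retreatment is at the investigator's discretion, so those subjects need not resemble the rest. DAS28-CRP change and ACR20/50/70 at weeks 40 and 48 are listed secondary efficacy endpoints (SAP 4.2.2), although they are descriptive (Protocol 12.6.6). For labs, vital signs and Ig, scheduled records are relabelled or left out of the by-visit summaries.

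**Working it through.** **Reproducing the SAP targets.** Target day = 7 × week + 1 gives 169, 183, 211, 281 and 337 for weeks 24, 26, 30, 40 and 48, as the SAP states. The efficacy week-40 window, days 211 to 308, has 308 − 211 + 1 = 98 days, also as stated. Week 16 is day 113.

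**Inputs.** R is the study day of the first infusion of the second dose. From Protocol 9.12 to 9.15, weeks 26, 30, 40 and EOS fall on R + 14, R + 42, R + 112 and R + 168. SAP windows:

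- Efficacy: week 24 = 106–210; week 40 = 211–308; week 48 from 309.
- Labs: week 24 = 106–175; week 26 = 176–196; week 30 = 197–245; week 40 = 246–308; week 48 from 309.
- Vital signs: as labs, but with no window for 246–308.
- ADA: week 24 = 106–175; week 30 = 197–245; week 48 from 309; no window for 176–196 or 246–308.
- CD19/Ig: week 24 = 106–210; week 48 from 309; no window for 211–308.

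**Mapping on nominal days**

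| Record | R | Study day | Result |
|---|---|---|---|
| Week-26 labs, vital signs | 113–161 | 127–175 | week-24 window, barred: dropped |
| Week-30 vital signs | 113–133 | 155–175 | week-24 window, barred: dropped |
| Week-30 vital signs | 134–154 | 176–196 | labelled week 26 |
| Week-30 ADA | 113–133 | 155–175 | week-24 window, barred: dropped |
| Week-30 ADA | 134–154 | 176–196 | no window: dropped |
| Week-40 efficacy | 113–140 | 225–252 | week-40 window, loses to EOS |
| Week-40 labs | 113–133 | 225–245 | week-30 lab window |
| Week-40 labs | 134–140 | 246–252 | week-40 window, loses to EOS |
| EOS efficacy, labs | 113–140 | 281–308 | labelled week 40; week 48 empty |
| EOS ADA, vital signs, Ig | 113–140 | 281–308 | no window: dropped |

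EOS displaces the true week-40 efficacy visit because it lies 0 to 27 days from target 281, against 56 to 29 days for the true visit. For R = 113–140 no scheduled ADA sample after the second dose receives an analysis visit.

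The week-40 labs with R = 113–133 need care. The lab table's footnote a says "Laboratory parameters will only be included at the visits where it is scheduled for assessment in the output tables". Protocol 9.13 lists vital signs and "collection of PK samples and samples for antidrug antibodies" at week 30, with no chemistry or hematology. On that reading these labs are not printed; if week 30 is printed, they appear there under the wrong label.

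**Upper edge.** For R = 162–175 every scheduled visit maps correctly. Footnote a also allows a delay ("An infusion may be delayed up to 7 days to allow for recovery from infection"), so R can reach 169 + 7 = 176. The pre-infusion week-24 labs and vital signs then fall on day 176, in the week-26 window. They tie with day 190 around target 183 (7 days each way) and lose to the later visit. The day-176 ADA sample has no window.

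**With visit tolerances** (EOS ±2 days, week 40 ±3, week 30 ±2, week-26 infusion delayed 0 to 7 days):

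- Efficacy week 48 empty: certain if R + 170 ≤ 308, so R ≤ 138; possible if R + 166 ≤ 308, so R ≤ 142.
- Week-30 ADA lost: certain if R + 44 ≤ 196, so R ≤ 152; possible to 156.
- Week-40 labs in the week-30 window: certain if R + 115 ≤ 245, so R ≤ 130; possible to 136.
- Week-26 labs lost: certain if R + 21 ≤ 175, so R ≤ 154; possible to 161.

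**The case against.** The best defence is that the SAP windows are calendar time since baseline. With R = 113, EOS falls on day 281, which is 40 weeks after the first infusion, and an empty week 48 truthfully shows that nobody observed that subject at 48 weeks. Re-anchoring mixes times since baseline according to an event after randomization. That trade-off is real and needs a footnote. It does not explain why protocol-scheduled ADA, Ig and vital-sign records receive no visit at all, or why the same SAP ties its PK windows to the second dose.

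Efficacy also has the analysis that excludes early retreatment. That helps, but it does not repair the all-subjects analysis that SAP 9.7 also requires. For the pooled-reference Day 1 to EOS DAS28-CRP comparison, Appendix 6 lists only full-analysis and per-protocol tables, and the per-protocol definition does not exclude early retreatment.

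The safety effect is limited, and this stands. Lab shift and grade ≥ 3 tables use all post-baseline results. ADA incidence by period does not depend on these windows. SAP 9.8.5 promises ADA by visit, yet the ADA tables in Appendix 6 are titled by period only, so the ADA loss matters only if that display is produced.

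A reader might also infer bias between arms. The documents do not support that: the same mapping applies to all three blinded arms, and nothing shows that early retreatment differs between them.

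**Conclusion.** The mismatch is real and worth correcting, but its reach is descriptive. It affects all-subjects Day 1 to EOS efficacy at weeks 40 and 48, by-visit lab, vital-sign and Ig summaries, and by-visit ADA if produced.

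A reader might infer that the trial's main conclusions are at risk. They are not. The week-24 DAS28-CRP equivalence test uses only data up to the first infusion of the second dose, and primary PK comes from the first-dose profile. Nor does it follow that early-retreated subjects' week-40 labs certainly vanish from the tables. That rests on reading week 30 as a visit without scheduled labs; the SAP lab table itself has a week-30 row, the extracted Table 1 is hard to read at that point, and the table shells are in a separate document.

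The ranges above are retreatment days, not subject counts. The documents give neither the rate nor the timing of early retreatment, so the number affected is unknown and may be small. For scale, each 1% of the 300 retreated on days 113 to 138 is 3 subjects missing from week 48.

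**What to change.** For subjects who receive a second dose, define the non-PK windows after it by days since its first infusion, as the current bounds minus 169:

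- Efficacy: week 40 = +42 to +139.
- Labs and vital signs: week 26 = +7 to +27.
- Vital signs, ADA and, if scheduled, labs: week 30 = +28 to +76.
- Labs: week 40 = +77 to +139.
- All five tables: week 48 from +140.

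Targets become +14, +42, +112 and +168. Assign pre-infusion records on the day of that first infusion to week 24, even when the day is after 175; otherwise the day-176 loss remains. Keep the Day-1 windows for all other earlier records and for subjects with no second dose.

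With the protocol tolerances, the visits fall at +14 to +21, +40 to +44, +109 to +115 and +166 to +170, each inside its own window whatever R is. A subject retreated on day 169 maps exactly as now.

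The price in interpretation is that, for early-retreated subjects, weeks 40 and 48 mean 16 and 24 weeks after retreatment, not calendar weeks. Footnote this, and keep the subgroup without early retreatment beside the all-subjects efficacy results. The work is limited to the SAP window tables, the dataset derivation and the footnote; visits and data collection do not change.

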### **FOR PK ANALYSES:**

Scheduled Sample Visit	Window Mapping
Day 1 Pre-dose	Prior to the 1st IP infusion of 1st dose start time but on the same day
Day 1 End of infusion	within 10 minutes of 1st infusion of 1st dose stop date/time
Day 1 3 hours	3 hr $\pm$ 10 minutes after 1st IP infusion of 1st dose stop date/time
Day 1 6 hours	6 hours $\pm$ 10 minutes after 1st IP infusion of 1st dose stop date/time

Sponsor: Amgen Inc.

Statistical Analysis Plan

Protocol No: 20130108

10-December-2018/ Version 2.0

Day 2 24 hours post-dose	24 hr $\pm$ 3 hours after 1st IP infusion of 1st dose stop date/time
Day 3 48 hours post-dose	48 hr $\pm$ 3 hours after 1st IP infusion of 1st dose stop date/time
Day 15 Pre-dose	Prior to the 2nd IP infusion of 1st dose start time but on the same day
Day 15 End of infusion	within 10 minutes of 2nd infusion of 1st dose stop date/time
Day 15 3 hours	3hr $\pm$ 10 minutes after 2nd IP infusion of 1st dose stop date/time
Day 15 6 hours	6hr $\pm$ 10 minutes after 2nd IP infusion of 1st dose stop date/time
Day 16 24 hours post-dose	24 hr $\pm$ 3 hours after 2nd IP infusion of 1st dose stop date/time
Day 17 48 hours post-dose	48hr $\pm$ 3 hours after 2nd IP infusion of 1st dose stop date/time
Week 4	2 wks (14 days) $\pm$ 2 days after the 2nd infusion of 1st dose stop date
Week 8	6 wks (14 days) $\pm$ 2 days after the 2nd infusion of 1st dose stop date
Week 12	10 wks (14 days) $\pm$ 2 days after the 2nd infusion of 1st dose stop date
Week 24 Pre-dose	Prior to the 1st IP infusion of 2nd dose start time but on the same day
Week 26 Pre-dose	Prior to the 2nd IP infusion of 2 nd dose start time but on the same day
Week 30	4 wks (28 days) $\pm$ 2 days from the 2nd infusion of 2nd dose stop date
Week 48	22 wks (154 days) $\pm$ 2 days from the 2nd infusion of 2nd dose stop date

### FOR EFFICACY ANALYSES:

Study Analysis Visit	Target Day	Study Day	Interval (days)
Baseline	1	$\leq 1$	NA
Week 8	57	2 – 70	69
Week 12	85	71 – 105	42
Week 24	169	106 – 210	98
Week 40	281	211 – 308	98
Week 48	337	$\geq 309$	NA

Sponsor: Amgen Inc.

Statistical Analysis Plan

Protocol No: 20130108

10-December-2018/ Version 2.0

**FOR SAFETY (HEMATOLOGY AND CHEMISTRY) ANALYSES:**

Study Analysis	Target Day	Study Day	Interval (days)
Visita			
Baseline b	1	≤1	NA
Week 2	15	2 – 16	15
Day 17	17	17	1
Week 4	29	18 – 42	25
Week 8	57	43 – 105	70
Week 24	169	106 – 175	63
Week 26	183	176 – 196	21
Week 30	211	197 – 245	49
Week 40	281	246 – 308	63
Week 48	337	≥309	NA

a Laboratory parameters will only be included at the visits where it is scheduled for assessment in the output tables.

b If a subject has lab measurements on the same day as the first infusion date of first dose but at a time after the first infusion of first dose is administered, the lab measurements will not be defined as baseline, but as Week 2 measurements.

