9.2 Baseline (Day 1, first day of treatment, Week 0)

Day 1 will be defined as the first day of treatment. After subjects are confirmed to meet the entry criteria ([Section 8.4](#)), the Investigator (or designee) will contact the IXRS to randomize the subject centrally to receive either ABP 798, rituximab (US), or rituximab (EU). The following assessments/procedures will be performed before treatment:

- subjective assessments (Subject's Global Health Assessment, subject's assessment of pain, and HAQ-DI, [Section 17.4](#)); subjective assessments will be the first assessments performed at the visit
- physical examination, including evaluation of body systems
- vital signs (systolic and diastolic blood pressure, pulse, respiration rate, and temperature)
- baseline joint assessments (DAS and ACR tender/swollen joint counts; [Section 17.3](#))
- Investigator's Global Health Assessment
- clinical laboratory testing, including serum chemistry, hematology, and CRP
- urinalysis and urine pregnancy test (for women of childbearing potential)
- collection of pretreatment PK samples (within 1 hour predose) and samples for pretreatment antidrug antibodies, CD19+ cell count, and IgA, IgG, and IgM levels

Any changes in concomitant medications since the last assessment will be recorded.

Any pretreatment AEs will be recorded as medical history; any pretreatment SAEs will be recorded using the eCRF. SAEs will be reported as outlined in [Section 11.2.2](#).

After completion of pretreatment procedures, ABP 798, rituximab (US), or rituximab (EU) will be administered as an IV infusion in a double-blinded fashion. Starting at the time of first treatment, all AEs, including increases in severity or frequency of pre-existing conditions, will be recorded in the eCRF.

At the end of infusion (EOI), blood samples for serum chemistry and hematology will be drawn.

At EOI and 3 and 6 hours after EOI, the following assessments will be performed:

- vital signs (systolic and diastolic blood pressure, pulse, respiration rate, and temperature)
- collection of PK samples (within 10 minutes after the end of the infusion, \pm 10 minutes at 3 and 6 hours)

Subjects may leave the site after the 6-hour post-EOI assessment. Subjects will continue on their stable MTX regimen.

9.3 Day 2

On day 2, approximately 24 hours after EOI, a PK sample (\pm 3 hours) and samples for CD19+ cell count and IgM levels will be collected. Subjects will continue on their stable MTX regimen.

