**FOR VITAL SIGNS ANALYSES:**

Study Analysis	Target	Study Dayb	Interval
Visita	Day		(days)
Baseline	NA	Day 1 prior to infusion	NA
Day 1 end of infusion (EOI)	NA	Day 1 after infusion	NA
Day 1 3 hours	NA	Day 1 3 hours after EOI	NA
Day 1 6 hours	NA	Day 1 6 hours after EOI	NA
Week 2	NA	Day 15 prior to infusion	14

Sponsor: Amgen Inc.

Statistical Analysis Plan

Protocol No: 20130108

10-December-2018/ Version 2.0

Day 15 EOI	NA	Day 15 after infusion	NA
Day 15 3 hours	NA	Day 15 3 hours after EOI	NA
Day 15 6 hours	NA	Day 15 6 hours after EOI	NA
Week 24	169	106 – 175	63
Week 26	183	176 – 196	21
Week 30	211	197 – 245	49
Week 48	337	≥309	NA

aIf a visit date with multiple records, the highest value per parameter will be selected for analysis.bDay 1 and Day 15 visit/timepoint are directly associated with infusion date/time.**FOR ADA ANALYSES:**

Study Analysis Visit	Target Day	Study Day	Interval (days)
Baseline a	1	≤1	NA
Week 2	15	2 – 16	15
Week 24	169	106 – 175	63
Week 30	211	197 – 245	49
Week 48	337	≥309	NA

aIf a subject has ADA assessments on the same day as the first infusion date of first dose but at a time after the first infusion of first dose is administered, the ADA assessments will not be defined as baseline, but as Week 2 assessments.

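### The scheduled day-1 end-of-infusion labs have no analysis row and are assigned to Week 2, and the Week 2 and Day 17 lab windows do not follow a delayed second infusion

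*SAP*

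**What the plan says.** The protocol sets three early chemistry and hematology draws after the baseline sample:

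- **Day 1 EOI** (Protocol 9.2): "At the end of infusion (EOI), blood samples for serum chemistry and hematology will be drawn".
- **Before infusion 2** (Protocol 9.5), at the day 15 visit.
- **About 48 hours after infusion 2** (Protocol 9.7), at the day 17 visit.

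Infusion 2 can move. Footnote a of Protocol Table 1 states: "An infusion may be delayed up to 7 days to allow for recovery from infection".

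The hematology and chemistry table in SAP 5.1 has rows for Week 2 (target day 15, days 2–16), Day 17 (day 17 only) and Week 4 (target day 29, days 18–42), but none for Day 1 EOI. Footnote b covers samples taken after the infusion on the first infusion date: "the lab measurements will not be defined as baseline, but as Week 2 measurements". Footnote a prints a parameter only at visits where it is scheduled.

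The clock starts at infusion 1: "Study day is defined as the number of days from Study Day 1". If several records share a window, "the visit closest to the target day with non-missing data will be considered for analysis". The tie rule is: "If two actual visit dates are at the same distance from the target day, the latest visit with non-missing data will be considered for analysis".

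Vital signs are handled differently in the same section. They have their own EOI rows, and a footnote says "Day 1 and Day 15 visit/timepoint are directly associated with infusion date/time". The PK table defines its Day 17 time point as 48 hours after the end of infusion 2.

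**The concern.** A scheduled draw is sent to a row whose target is two weeks later and whose own window, days 2–16, excludes the day of the draw. That sample is taken straight after an infusion and its premedication. The Week 2 sample is meant to be taken before an infusion. They are not interchangeable.

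The two later draws move with infusion 2, but their rows do not, and the Day 17 row is one day wide. When infusion 2 is late, a by-visit lab table can therefore show a value under the wrong label or leave it out. At stake is how the by-visit summaries of values and changes from baseline read around the first two infusions. No test or decision rule depends on them.

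**Working it through.** **Inputs.** Windows, targets, footnotes and selection rules are from SAP 5.1. Draw times are from Protocol 9.2, 9.5 and 9.7. The permitted delay of up to 7 days gives infusion 2 on days 15 to 22. Assumptions: the EOI sample falls on study day 1, the 48-hour draw falls on infusion day + 2, and there are no unscheduled samples.

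**The plan's own figures.** Window length is last day − first day + 1. Week 2: 16 − 2 + 1 = 15. Day 17: 17 − 17 + 1 = 1. Week 4: 42 − 18 + 1 = 25. All three agree with the table. (Two later rows do not: Week 8, days 43–105, is 63 days but is stated as 70; Week 24, days 106–175, is 70 but is stated as 63. This does not affect the present point.)

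**When the EOI value is selected.** Its distance from the Week 2 target is |1 − 15| = 14. The farthest that any other sample in days 2–16 can be is |2 − 15| = 13. So the EOI value loses to any other sample in the window and is selected only when there is none.

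**Mapping by day of infusion 2.**

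| Infusion 2 | 48-hour draw | Week 2 row shows | Day 17 row shows | Falls in Week 4 window |
|---|---|---|---|---|
| Day 15 | Day 17 | Pre-infusion value (distance 0 against 14) | 48-hour value | None |
| Day 16 | Day 18 | Pre-infusion value (distance 1 against 14) | Empty | 48-hour draw |
| Day 17 | Day 19 | Day-1 EOI value | Pre-infusion value | 48-hour draw |
| Days 18–22 | Days 20–24 | Day-1 EOI value | Empty | Both draws |

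In the last line the 48-hour draw is always the closer of the two to day 29. With infusion 2 on day 18, the distances are 29 − 18 = 11 and 29 − 20 = 9. With infusion 2 on day 22, they are 7 and 5. The pre-infusion value is then not selected for any row.

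If infusion 2 is on day 15 but the pre-infusion sample is missing, Week 2 shows the EOI value and Day 17 is still correct.

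The delay allowance does not cover an early infusion. For completeness, infusion 2 on day 14 gives draws on days 14 and 16, each 1 day from target. The tie rule then puts the post-infusion value in Week 2 and leaves Day 17 empty.

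**Whether Week 4 would be printed.** The Week 4 visit text (Protocol 9.8) lists PK, CD19+ and immunoglobulin samples, but no chemistry or hematology. Under footnote a, values in the Week 4 window may therefore be suppressed rather than shown. Protocol Table 1 is too broken in the available text to settle this.

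**The case against.** The strongest reply is that footnote b does its main job, which is to keep post-dose values out of baseline. The same device appears in the ADA table (mapped to Week 2) and the CD19+/immunoglobulin table (mapped to Day 2). For an on-schedule subject nothing is misreported: Week 2 shows the true pre-infusion value and Day 17 the true 48-hour value. The by-visit tables are descriptive. SAP 9.8.3 builds the shift tables and the grade 3 or higher outputs from all post-baseline results, scheduled or not, so EOI and 48-hour values count there. The rule is the same in every arm.

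Most of this stands and limits the point. The parallel with the ADA and CD19+ tables does not remove it: Protocol 9.2 schedules no post-infusion sample for those measures on day 1, whereas chemistry and hematology are scheduled.

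A reader might infer more than the documents support:

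- *That Week 2 is wrong for everyone.* For on-schedule subjects the EOI value is omitted, not misreported.
- *That post-infusion labs never appear.* The Day 17 row shows the 48-hour value when infusion 2 is on day 15.
- *That any shift from day 15 spoils the pre-infusion value.* With infusion 2 on day 16 it is still in the right row.
- *That late 48-hour values are printed as Week 4.* Footnote a may suppress them.
- *That the comparison between arms is biased.* Nothing in the documents shows a differential effect.

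**Conclusion.** The point holds, with minor severity. The missing row applies to every subject with a day-1 EOI sample, about 300 by plan. For those on schedule, the consequence is only that a scheduled value appears in no by-visit table. Mislabelled or lost values arise when infusion 2 is off day 15 or the pre-infusion sample is missing. Across the permitted days 15 to 22, day 15 is the only one of eight on which both infusion-2 draws reach their own rows. From day 17 on, Week 2 shows the day-1 EOI value.

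The effect is confined to the by-visit lab summaries, Tables 14-7.1.1 to 14-7.1.3 and 14-7.2.1 to 14-7.2.3. The share of subjects off day 15 is not given, so the number of affected values cannot be computed. The mapping rests on the assumptions listed with the inputs; an extra sample in days 2–16 would keep the EOI value out of Week 2.

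**What to change.** In the hematology and chemistry table of SAP 5.1:

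1. Add a Day 1 EOI visit for samples taken after infusion 1 on the first infusion date, and delete the mapping to Week 2 in footnote b.
2. Define Week 2 as the last sample taken after the day of infusion 1 and before infusion 2. The lower limit keeps the EOI sample out when the pre-infusion sample is missing.
3. If infusion 2 is missed, as SAP 5.1 defines it, keep the calendar window of days 2–16 for Week 2.
4. Define Day 17 as the sample about 48 hours after infusion 2, following the PK table. The vital-signs table is a model for the EOI row but has no 48-hour row.
5. Give these infusion-based rows precedence over the Week 4 window, so that a sample used in one of them is not also a candidate for Week 4.

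The cost is SAP wording, slightly more programming and one extra row in the by-visit tables. No new data are needed, and the primary PK and efficacy analyses are untouched.
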